**Table 4 Analysis Visit Names**

Visit Name	AVISIT	Study Group
Visit 1 Day 1	BASELINE	All study groups
Visit 2 Day 31	AVISIT 4	MenACWY

Visit 2 Day 31	AVISIT 2	All study groups except MenACWY
Safety Call D15	SAFETY CALL 1	All study groups
Visit 3 Day 61	AVISIT 3	All study groups except MenACWY
Visit 4 Day 91	AVISIT 4	All study groups except MenACWY
Safety Call D75	SAFETY CALL 2	All study groups except MenACWY

### Titer Results

For a given subject and a given immunogenicity measurement, missing or non-evaluable measurements will not be replaced. Summaries and analyses for the pooled B serogroup strains will be performed using all available non-missing titer results. Subjects who have at least one non-missing titer result from the four possible serogroup B strains at a single visit will be included in the summaries and analyses for the pooled serogroup B strains.

Titer results recorded as below the LOD will be imputed with a numeric value of half the LOD for summaries and analyses and will be listed as reported in the raw data. For example, if an assay records a LOD of 80 and a sample is reported to have “< 80” as the titer level, a value of 40 will be used for the statistical summaries and analyses. Titer results recorded as “1:x” (where x is the dilution factor) will be assigned a numeric value of x. Titer results recorded as “>1:x” will be assigned a numeric value of x.

LOD and LLOQ values will be defined in the Clinical Study Report (CSR).

### Missing Data

For safety analyses, subjects who missed reporting symptoms (solicited or unsolicited) or concomitant medications will be analyzed to determine the missing mechanism. For the analysis of solicited symptoms, implausible measurements will not be replaced but they will be excluded from the analyses. Missing values will not be imputed for solicited/unsolicited AEs or concomitant medications.

In order to minimize the effect of missing data, the study period will be divided into time intervals for the safety analyses. For unsolicited AEs, the study period will be divided into the following intervals: all unsolicited AEs reported from day 1 to day 31 after vaccination (day of vaccination = day 1, Visit 1 and Visit 3 will be assessed separately and combined), medically attended AEs reported during the entire study period, AEs leading to premature withdrawal from the study during the entire study period, SAEs reported during the entire study period and AESI reported during the study period for the Unsolicited Safety Set.

Concomitant medications will be assessed for the entire study period for the Overall Safety Set.

Solicited AE data will be analyzed by the following intervals: 30 minutes post-vaccination on day of vaccination, 1 – 3 days post-vaccination (including the day of vaccination as day 1, excluding 30 minutes post-vaccination), 4 days – 7 days post-vaccination, and 1 day - 7 days (including the day of vaccination as day 1, excluding 30 minutes post-vaccination). Intervals will be assessed for Visit 1 and Visit 3, separately and combined, for the Solicited Safety Set. Solicited local AEs will be considered separately by vaccine for study groups where two vaccinations are administered at each visit, and also separately by location

A subject will be classified as having missing data within the specified intervals as described below:

- Solicited AEs
  - Temperature will be regarded as missing if “Temperature taken” = “No” at every time point within the interval (on Post-vaccination Body Temperature eCRF page).
  - Pain will be regarded as missing if no intensity values are recorded for Vaccine A and Vaccine B separately at every time point within the interval (on Vaccine A/Vaccine B Solicited Local Adverse Event eCRF pages). An intensity value of ‘None’ is a valid value and will not be considered a missing value.
  - Erythema, swelling and induration will be regarded as missing if no measurements in mm are recorded for Vaccine A and Vaccine B separately at every time point within the interval (on Vaccine A/Vaccine B Solicited Local Adverse Event eCRF pages).
  - Nausea, myalgia, arthralgia, headache and fatigue will be regarded as missing if no intensity values are recorded at every time point within the interval (on Solicited General Adverse Events eCRF page). An intensity value of ‘None’ is a valid value and will not be considered a missing value.
- Unsolicited AEs
  - Non serious AEs will be regarded as missing if no AEs are recorded during the interval and there is no response to “Did the subject experience any non-serious adverse events during the study?” (Non Serious Adverse Event YN eCRF page).
    - Medically attended AEs will be regarded as missing if, in addition to the missing criteria for non-serious AEs, there is no response to “Medically attended visit” (Non Serious Adverse Events eCRF page).

- AEs leading to withdrawal from the study will be regarded as missing if, in addition to the missing criteria for non-serious AEs, there is no response to “Did the subject withdraw from the study as a result of AE?” (Non Serious Adverse Events eCRF page).
- Serious AEs will be regarded as missing if no SAEs are recorded during the interval and there is no response to “Did the subject experience a serious adverse event or a non-serious AESI during the study?” (Serious/Expedited Event YN eCRF page), or “Did the subject experience a serious adverse event or a non-serious AESI during the study?” = “Yes” and there is no response to “Serious” (Serious/Expedited Event eCRF page).
- AESI will be regarded as missing if there is no response to “Did the subject experience any arthritis/arthralgia (joint pain) events during the study?” (Arthritis/Arthralgia (Joint Pain) Events YN eCRF page).
- Concomitant medications will be regarded as missing if no concomitant medications are recorded on the Concomitant Medications eCRF page, and there is no response to “Were any medications taken?” on the Concomitant Medications YN eCRF page.

The following algorithm will be applied to each interval:

1. If less than 20% of subjects are without any solicited AE/unsolicited AE/concomitant medication data (i.e. no solicited AE/unsolicited AE/concomitant medication data have been captured) for the respective data/visit/time interval, then no assumptions will be made about the missing mechanism.
2. If 20% or more of subjects are without any solicited AE/unsolicited AE/concomitant medication data, the missing mechanism will be analyzed using a newly created variable indicating whether a subject has any respective data values or not.
  - a. If the percentage of missing subjects does not vary significantly between study groups (Fisher’s Exact  $p \geq 0.05$ ) then ‘missing completely at random’ (MCAR) is assumed.
  - b. If the percentage of missing subjects varies significantly between study groups (Fisher’s Exact  $p < 0.05$ ) then ‘missing at random’ (MAR) is assumed, i.e., the missing mechanism is conditional on the vaccine group. The denominator used to calculate percentages will be reduced by the number of subjects with missing values to reduce bias through inflated ‘no AE’ counts.

The number and percentage of subjects with no data recorded for each time interval specified for solicited AEs, unsolicited AEs and concomitant medications will be presented in a table for the All Enrolled Set, along with the p-value for Fisher's Exact test.

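### SAP 4.3 judges missing unsolicited AE data after each dose from a study-wide item, and its rules for medically attended and withdrawal AEs can never flag a blank item

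*SAP*

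**What the plan says.** SAP 4.3 (Missing Data) divides the safety follow-up into intervals. For all unsolicited AEs the interval is days 1 to 31 after vaccination, and "Visit 1 and Visit 3 will be assessed separately and combined". Other categories use one long interval, for example "medically attended AEs reported during the entire study period"; AEs leading to withdrawal and SAEs are treated in the same way.

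The rules for calling a subject missing within an interval are:

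- Non-serious AEs: "Non serious AEs will be regarded as missing if no AEs are recorded during the interval and there is no response to" the yes/no item "Did the subject experience any non-serious adverse events during the study".
- Medically attended AEs: "Medically attended AEs will be regarded as missing if, in addition to the missing criteria for non-serious AEs, there is no response to" the medically attended visit item on the Non Serious Adverse Events page.
- Withdrawal AEs: "AEs leading to withdrawal from the study will be regarded as missing if, in addition to the missing criteria for non-serious AEs, there is" a blank in the withdrawal item on that same page.
- SAEs: "Serious AEs will be regarded as missing if no SAEs are recorded during the interval and there is no response to" the corresponding yes/no item. A second clause, joined by or, catches a yes on that item with the seriousness field left empty.

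The algorithm is then run for each interval. Below 20% missing, nothing is assumed. "If 20% or more of subjects are without any solicited AE/unsolicited AE/concomitant medication data, the missing mechanism will be analyzed" by comparing study groups with Fisher's exact test. At p<0.05 the data are taken as missing at random and the denominator is reduced, with the stated aim of avoiding inflated counts of subjects without AEs. The missing percentages and Fisher p-values are tabulated for the All Enrolled Set.

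**The concern.** There are two separate faults.

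**Unobserved time after a dose.** The classification is made per post-dose interval, but the deciding item covers the whole study. It cannot show whether anyone spoke to the subject after Visit 3. The solicited AE rules in the same section look at entries at each time point within the interval, so they do not share this weakness. Nor does the analysis set remove such subjects. Under SAP 4.4.3 a single contact after any vaccination is enough for the Unsolicited Safety Set, and a subject who attended Visit 2 already has that. Under SAP 4 the default denominator is everyone in the group in that set.

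**Blank items on a recorded AE.** The added condition in the medically attended and withdrawal rules refers to a field that exists only when an AE has been entered, yet it is attached to a criterion requiring that none has been entered.

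Protocol 10.6 says that missing safety values will not be imputed and leaves the analysis of the missing mechanism to the SAP. If the flag misses dosed but unobserved subjects, they are absent from the reported missing percentage, the Fisher table and the count toward the 20% trigger, and they are treated as having had no event.

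**Working it through.** The plan states no figure on this point, so the check is of the logic, followed by an illustration.

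**Step 1. Write out the rules (inputs: SAP 4.3).** Let A = an AE is recorded in the interval, Y = the study-level item is answered, R = the item on the AE page is answered (it exists only if A holds). The parent rule is: not A and not Y. The medically attended and withdrawal rules as written are: not A, not Y and not R. An explicit or version is: (not A and not Y), or (A and not R).

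| AE recorded | Study item | AE-page item | Parent rule | Sub-rule as written | Sub-rule with explicit or |
|---|---|---|---|---|---|
| No | Blank | No row | Missing | Missing | Missing |
| No | Answered | No row | Not missing | Not missing | Not missing |
| Yes | Blank | Blank | Not missing | Not missing | Missing |
| Yes | Blank | Answered | Not missing | Not missing | Not missing |
| Yes | Answered | Blank | Not missing | Not missing | Missing |
| Yes | Answered | Answered | Not missing | Not missing | Not missing |

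The parent and as-written columns are identical. Whenever the parent criteria are met there is no AE row, so R is necessarily blank and the extra condition has no effect. The two patterns it might have caught, an AE recorded with the item blank, are never flagged.

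**Step 2. Apply the parent rule after Visit 3.** Take a subject with an AE after dose 1, dose 2 given at Visit 3, and no contact afterwards. A consistent eCRF has the study-level item answered yes. The subject falls in the second row: not flagged, and event-free after Visit 3. Changing and to or does not help here, because the second row is unchanged in the last column. If the item had been blank, the subject would be in the first row and flagged.

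**Step 3. Size, by illustration.** Assumptions, none given in the documents: true AE risk p in the interval; a share m of dose-2 recipients unobserved, with the study-level item answered and no AE recorded in the interval; the same risk in observed and unobserved subjects. Displayed rate = p × (1 − m).

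| p | m = 5% | m = 10% | m = 20% |
|---|---|---|---|
| 20% | 19.0% | 18.0% | 16.0% |
| 30% | 0.30 × 0.95 = 28.5% | 0.30 × 0.90 = 27.0% | 0.30 × 0.80 = 24.0% |
| 40% | 38.0% | 36.0% | 32.0% |

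The flagged share of these subjects is 0% in every cell.

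**Step 4. What the present algorithm would do with a correct flag.** At m = 5% or 10% the share is below 20%, no denominator changes, and 28.5% and 27.0% remain. At m = 20% the trigger is reached, but the SAP states a denominator reduction only if Fisher p<0.05 as well. Removing unobserved subjects directly gives 28.5/95 = 27.0/90 = 24.0/80 = 30.0%.

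**The case against.** Several points on the other side stand.

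- A reader might infer that the check will show almost no missing data after dose 2 whatever the loss. The documents do not support that. They do not say when the study-level item is completed or what is entered for a lost subject; with the item blank and no AE in the interval, the subject is flagged.
- A reader might also put the whole dilution in the table down to the flag. Step 4 shows otherwise: at 5 to 10% loss, the 20% threshold alone would leave it.
- No comparison of the post-Visit 1 and post-Visit 3 windows is planned. SAP 9.1.2 gives separate summaries, and Protocol 10.10 calls all analyses descriptive.
- Loss after dose 2 is visible elsewhere: SAP 7.2.2 tabulates attendance at Safety Call 2 and Visit 4. Withdrawal reasons are recorded under Protocol 9.2.1 and summarised under SAP 5.1. Protocol 8.3.3.4 requires medical attention to be recorded for each symptom, and eCRF omissions may be queried (Protocol 11.1). Blank items that survive cleaning may be few.
- The phrase joining the sub-rules could be meant loosely, as a further route to missing. But the SAE rule shows that the SAP writes or when it means it. A bare or would also misfire: if having no AE row counts as no response, every subject without an AE would be flagged. The text needs clarifying on either reading.

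These points limit the size and reach of the concern. They do not make the stated rules work.

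**Conclusion.** The concern holds as a fault in the stated rules. For all unsolicited AEs, a subject dosed at Visit 3 and then lost, with the study-level item answered and no AE recorded in the interval, is counted as observed and event-free. That subject is left out of the missing percentage, the Fisher test and the 20% trigger. For medically attended and withdrawal AEs, which are assessed over the entire study period, the main fault is different: the sub-rules reduce to the parent rule and cannot detect a blank item on a recorded AE.

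How many subjects or items are affected cannot be known from the documents. The rates in the table rest on assumed loss and AE risks. Subjects who never received dose 2 are a separate matter. The effect is confined to descriptive safety summaries and the missing-data table; immunogenicity analyses and sample size are untouched. This is a minor point, worth correcting because the repair is cheap.

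**What to change.** In SAP 4.3:

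1. Keep the present criterion for non-serious AEs and add an alternative: or no AE with onset in the interval is recorded and no safety call or visit took place after that dose. It should be added, not substituted. A contact test alone would stop flagging a subject who attended but whose AE pages were left blank, and that subject is caught today.
2. For the post-Visit 3 summary, exclude from the denominator dosed subjects flagged as having no contact after that dose. State openly that this extends branch 2b, which now reduces denominators only at 20% or more missing with Fisher p<0.05. At 5 to 10% loss this step is what removes the dilution.
3. For medically attended AEs and AEs leading to withdrawal, define missing as: the non-serious AE missing criteria are met, or an AE is recorded and the item is blank.

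One limit remains: a subject reached at Safety Call 2 and lost afterwards still counts as observed for the whole interval.

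The cost is a few SAP sentences and a small programming change. Contact dates are already collected for SAP 7.2.2.

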### 10.6. Derived and transformed data

- Immunogenicity
  - The assay cut-off values will be defined by the laboratory before analysis and will be documented in a protocol amendment or in the clinical study report.
  - For the primary and secondary endpoints (see Section 10.1 and Section 10.2, respectively), the percentage of subjects with hSBA titers  $\geq$  LLOQ and with a

4-fold increase in hSBA titers against each of the *N. meningitidis* serogroup B test strains and against *N. meningitidis* serogroups A, C, W-135, and Y will be determined.

- The GMT calculations are performed by taking the anti-log of the mean of the log concentration/titer transformations. Values to be used for the antibody concentrations/titers below the assay cut-off will be described in the statistical analysis plan.
- Handling of missing data: for a given subject and a given immunogenicity measurement, missing or non-evaluable measurements will not be replaced.
- Reactogenicity and Safety
  - Handling of missing data: for safety analyses, subjects who missed reporting symptoms (solicited/unsolicited) or concomitant medications will be analyzed further. The main safety analyses will contain missing data (missing safety values will not be imputed) but further analyses to assess the missing mechanism will be specified in the statistical analysis plan.
  - For the analysis of solicited symptoms, missing or non-evaluable measurements will not be replaced. Therefore the analysis of the solicited symptoms based on the All Exposed Set will include only subjects/doses with documented safety data (i.e. symptom screen/sheet completed).
  - Solicited AEs will be assessed as described in [Table 12](#) and Section [10.9.2](#).

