**Table 2 Treatment Labels**

Treatment Number	Treatment Label
P	MenABCWY
P	rMenBOMV+ACWY_S 
P	rMenBOMV+ACWY_D 
P	rMenBOMV
P	MenACWY

S = same arm approximately 2.5cm apart, D= different arms

Categorical data will be described using the subject count and percentage in each category. A row denoted ‘Missing’ will be displayed to account for missing values categorical summaries. The ‘Missing’ row will only be displayed if at least one study group has a non-zero count for this category. Note percentages will not be displayed in the ‘Missing’ row, to draw attention to the percentages for the non-missing categories. Unless specified otherwise, percentages will be based on the number of subjects in each study group within the analysis population. Percentages will not be displayed if the count for a study group is zero, in order to draw attention to the percentages for non-zero counts. Percentages will be displayed using one decimal place.

Continuous data will be described using descriptive statistics (i.e. n, mean, standard deviation, minimum and maximum). For the summary statistics of all numerical variables unless otherwise specified, minimum and maximum will be displayed to the same level of precision as reported. Mean will be displayed to one level of precision greater than the data collected. Standard deviation/standard error will be displayed to two levels of precision greater than the data collected. P-values will be rounded to three decimal places. If a p-value is less than 0.001 it will be reported as “<0.001” If a p-value is greater than 0.999 it will be reported as “>0.999”.

If statistical analysis cannot be performed for a particular serogroup or study group, then these should be displayed as “NC.” (not calculated). Confidence intervals that cannot be calculated should be displayed as “(NC.)”.

Data will be displayed in all listings sorted by study group. Subjects will be identified in the listings by the subject identification number.

Serogroups should be displayed in the order in Table 3. If the combined B serogroups are to be presented in a table or listing, this group should be displayed last.

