#### **Solicited Safety Set (solicited local and systemic adverse events and other solicited adverse events)**

- All subjects in the All Exposed Set with any solicited AE data.

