### 7.2.1 Compliance

The number and percentage of subjects who received any study vaccination will be presented, as well as the number and percentage of subjects who received all expected vaccinations during the study and the number and percentage of subjects who withdrew from study vaccine. A subject has withdrawn from study vaccine if

- For all study groups except MenACWY:
  - Vaccination was administered at Visit 1, no vaccination was administered at Visit 3 and the subject has data recorded for at least one of the following: Safety Call D75; Visit 4 or
  - Vaccination was not administered at Visit 1 and vaccination was not administered at Visit 3 and the subject has data recorded for at least one of the following: Safety Call D75; Visit 4.
- For MenACWY study group:
  - No vaccination was administered at Visit 1 and the subject has data recorded for at least one of the following: Safety Call D15; Visit 2.

In addition, the number and percentage of subjects who did not receive all vaccinations with reason (including subjects who received a partial vaccination) will be displayed by visit. The number of expected vaccinations for each study group can be found in Table 5.

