#### Other solicited AEs

The use of analgesics/antipyretics (preferably paracetamol) for either prophylactic or treatment purposes will also be recorded as other solicited events in the pDiary and summarized with the solicited AEs.

Note: Any solicited AE that meets any of the following criteria will be entered into subjects' source document and also as an AE on the eCRF:

- Solicited local or systemic AE that continues beyond day 7 after vaccination.
- Solicited local or systemic AE that leads to a visit to a healthcare provider (medically attended AE).
- Solicited local or systemic AE leading to the subject withdrawing from the study or the subject being withdrawn from the study by the investigator (AE leading to withdrawal).
- Solicited local or systemic AE that otherwise meets the definition of an SAE.

Solicited AE's will be summarized according to the defined severity grading scales in Table 8. Body temperature will be classified as  $<38^{\circ}\text{C}$  (no fever) and  $\geq 38^{\circ}\text{C}$  (fever), as well as by  $0.5^{\circ}\text{C}$  increments from  $36.0^{\circ}\text{C}$  up to  $\geq 40^{\circ}\text{C}$ .

Missing values for solicited AEs will be handled as described in Section 4.3.

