Subjects with solicited AEs will be counted based on actual treatment received for each study group using the Solicited Safety Set. The following categories will be included in the summary table for solicited AE:

1. Subjects who experienced any solicited AE within 7 days of vaccination
2. Subjects who experienced any systemic solicited AE within 7 days of vaccination
3. Subjects who experienced any local solicited AE within 7 days of vaccination
4. Subjects who experienced any local solicited AE on upper left deltoid within 7 days of vaccination
5. Subjects who experienced any local solicited AE on lower left deltoid within 7 days of vaccination

6. Subjects who experienced any local solicited AE on upper right deltoid within 7 days of vaccination
7. Subjects who experienced any local solicited AE on lower right deltoid within 7 days of vaccination
8. Subjects who experienced any other solicited AE within 7 days of vaccination

Categories 1 - 8 will be repeated for the following time points:

- Within 30 minutes of vaccination
- Within 1-3 days of vaccination (excluding 30 minutes post-vaccination)
- Within 4-7 days of vaccination

The number and percentage of subjects experiencing each solicited AE will be presented for each symptom maximal severity (defined in Table 8) by study group, visit (Visit 1, Visit 3 and Any visit, with the MenACWY group only included for Visit 1 and Any visit), and time point (30 minutes post vaccination, days 1 to 3 excluding 30 minutes post vaccination, days 4-7, days 1-7 excluding 30 minutes post-vaccination). Local solicited AEs will also be presented by maximal severity and site of administration: upper or lower deltoid, left or right arm. Pain and fever will also be summarized by the use of antipyretics/analgesics for the prevention and/or treatment of pain/fever.

If a solicited AE occurs more than once for a subject within a time point, it will be counted in the summary only once, according to the maximal severity.

Solicited AEs will be listed and the use of antipyretics/analgesics will be highlighted.

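### Solicited AE rates by dose keep subjects without data in the denominator unless a 20% threshold and a Fisher test are both met (SAP 4.3), contrary to Protocol 10.6

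*SAP*

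**What the plan says.** Five provisions act together.

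- **SAP 9.1.1** has no denominator rule of its own for missing solicited data: "Missing values for solicited AEs will be handled as described in Section 4.3".
- **SAP 4.3, Missing Data** has three branches, applied to each interval. Branch 1 (under 20% of subjects without data): "then no assumptions will be made about the missing mechanism". Branch 2a (20% or more, Fisher p of at least 0.05): missing completely at random (MCAR) is assumed. Branch 2b (20% or more, Fisher p below 0.05): "The denominator used to calculate percentages will be reduced by the number of subjects with missing values to reduce bias through inflated" 'no AE' counts. Only 2b mentions the denominator.
- **SAP section 4** (text after Table 2) gives the default: unless something else is specified, "percentages will be based on the number of subjects in each study group within the analysis population".
- **SAP 9.1.1 and 4.4.3** fix the population for these tables: "Subjects with solicited AEs will be counted based on actual treatment received for each study group using the Solicited Safety Set". That set is "All subjects in the All Exposed Set with any solicited AE data", with no condition on dose or interval. Results are shown for Visit 1 and Visit 3 separately and combined.
- **Protocol 10.6** says that the analysis of solicited symptoms "will include only subjects/doses with documented safety data (i.e. symptom screen/sheet completed").

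SAP 7.2.1 expects some subjects to stop after the first dose. One of its definitions of withdrawal from study vaccine begins: "Vaccination was administered at Visit 1, no vaccination was administered at Visit 3 and the subject has data recorded" at a later contact.

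**The concern.** The population for the solicited tables is not specific to a dose, so a subject with first-dose diary data only belongs to it at Visit 3 as well. If the denominator is not reduced, that subject adds nothing to the numerator and one to the denominator. The subject is in effect counted as free of events after a dose that was not given or not documented.

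SAP 4.3 recognises this bias in branch 2b but makes the correction depend on a threshold and a p-value. Neither governs the bias, which equals the true rate times the missing share whether or not missingness differs between groups. The MCAR assumption in branch 2a justifies analysing the subjects who have data. It does not justify keeping those without data in the denominator.

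Safety and tolerability is a secondary objective, and solicited rates by dose are its main descriptive output. The error always understates reactogenicity. Groups with equal reactogenicity but unequal completeness at the second dose would show different rates.

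**Working it through.** The plan states no figure for this rule, so there is none to reproduce.

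**Step 1: which denominator applies.** SAP 9.1.1 refers to SAP 4.3. Branch 2b gives the number of subjects minus those missing. Branches 1 and 2a give nothing, so the SAP section 4 default applies: all subjects of the group in the Solicited Safety Set. Subjects with no solicited data at either dose are already outside that set. The problem therefore concerns rates by dose, symptom and interval, and is clearest at Visit 3.

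**Step 2: formula.** Let N be the group size in the set, m the share without data for the dose, and p the true rate, taken as equal in subjects with and without data.

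- Default denominator: shown rate = N(1 − m)p / N = p(1 − m). The shortfall is pm.
- Documented-data denominator: shown rate = N(1 − m)p / [N(1 − m)] = p.

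**Step 3: inputs.** N = 100 in each of the four two-dose groups (planned size). The rate p = 80% and all missing counts are assumptions. MenACWY is left out of Visit 3, as SAP 9.1.1 does for the AE tables. Fisher p-values are for the 2×4 table: exact in the first two rows, 1 for equal counts, simulated (200,000 draws) in the last three.

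| Missing per 100 | Overall missing | Fisher p | Branch | Shown rates |
|---|---|---|---|---|
| 3/5/7/9 | 24/400 = 6% | 0.31 | 1 | 77.6 / 76.0 / 74.4 / 72.8% |
| 5/10/15/19 | 49/400 = 12.25% | 0.013 | 1 | 76.0 / 72.0 / 68.0 / 64.8% |
| 25/25/25/25 | 100/400 = 25% | 1 | 2a | 60.0% in each group |
| 34/14/14/14 | 76/400 = 19% | about 0.0006 | 1 | 52.8 / 68.8 / 68.8 / 68.8% |
| 20/22/26/32 | 100/400 = 25% | about 0.23 | 2a | 64.0 / 62.4 / 59.2 / 54.4% |
| 15/20/25/35 | 95/400 = 23.75% | about 0.008 | 2b | 80% in each group |

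Example: with 19 missing, 80% × (1 − 0.19) = 64.8%. The documented-data denominator gives 80% in every row.

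In the second row missingness clearly differs between groups, yet the 20% gate blocks any correction and a spread of 76.0 − 64.8 = 11.2 points appears between groups with the same true rate. The last two rows have similar overall missingness, but the p-value decides whether 54.4% or 80% is printed for the fourth group, a difference that its own missing count (32 or 35) does not explain.

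**Step 4: other true rates.** At 19% missing, a true 30% shows as 24.3%, 50% as 40.5% and 90% as 72.9%.

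**Step 5: MenACWY at Visit 3.** SAP 4.3 does not say whether this single-dose group enters the Visit 3 missingness test. If it does, 100/500 = 20.0% are missing by design. That meets the threshold with Fisher p < 0.001 even when no one else is missing, and branch 2b applies.

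**The case against.** **The dilution is inferred.** SAP 4.3 is silent on the denominator in branches 1 and 2a, and the default in SAP section 4 yields where something else is specified. Protocol 10.6 might be that other specification, and SAP 4.3 says missing values are not imputed. But if documented-data denominators already applied everywhere, the reduction in 2b would have nothing to do. Stating it once, under two conditions, implies that the default holds elsewhere. At the least, the wording would lead an analyst following the SAP to the diluted rate.

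**Missing data are visible.** Categorical summaries carry a Missing row, 'None' is a recorded value distinct from missing, and missing counts are tabulated. A reader could therefore recompute the rate. This stands as mitigation, but the printed percentage stays diluted.

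**At Visit 3 the problem may not arise.** If MenACWY is counted, branch 2b applies by design. This stands as a limit. SAP 9.1.1 points the other way, because it records no second-dose solicited data for that group and leaves it out of the Visit 3 tables. A correction that depends on counting subjects who were never due a second dose is not a sound rule.

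**Populations differ.** The missingness table and its Fisher test use the All Enrolled Set, the AE tables the Solicited Safety Set. The examples use 100 per group for both, so their branch assignments are illustrative. The formula in Step 2 is unaffected.

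**The protocol conflict is narrow.** The Solicited Safety Set already removes subjects with no solicited data at all, so only the dose part of the Protocol 10.6 rule is breached. This is correct. For single symptoms and for Days 1–3, 4–7 and 1–7, the argument rests on the SAP's own definitions of missing and its stated aim of avoiding inflated 'no AE' counts.

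**Conclusion.** The concern holds. As written, the SAP understates solicited AE rates by dose whenever data are incomplete and the two conditions of branch 2b are not both met. At dose level this contradicts Protocol 10.6. The Visit 3 case assumes that MenACWY is kept out of the missingness test there.

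The shortfall is the true rate times the missing share. At an assumed 80% rate it is 2.4 to 7.2 points with 3% to 9% missing, and 20 points with 25% missing in branch 2a. The rate and the missing shares are assumptions, as is equal risk in subjects with and without data. With little missingness the effect is small.

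The results are descriptive and immunogenicity is untouched. This should be corrected, but it does not threaten the primary objective.

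**What to change.** Amend SAP 4.3 and 9.1.1 for solicited AEs, in all branches:

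1. In tables by dose, use as denominator the subjects with documented solicited data for that dose, as in Protocol 10.6.
2. In tables by symptom and interval, use subjects with at least one non-missing value for that symptom in that interval, by the definitions of missing already in SAP 4.3.
3. Keep the 20% threshold and Fisher test as a description of missingness that does not change any denominator.
4. State that MenACWY is left out of the Visit 3 missingness table and test. Make this change together with item 1: alone, it could move Visit 3 from branch 2b to the full denominator and make the dilution worse.

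The cost is SAP wording and denominator code, with no new data. The drawback is that denominators vary slightly between tables, so each table must show its own.
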